#### **12.2.5. Adverse events based on signs and symptoms**

All AEs spontaneously reported by the subject or reported in response to the open question from the study personnel: *“Have you had any health problems since you were last asked?”*, or revealed by observation will be collected and recorded in ClinBase.

When collecting AEs the recording of diagnoses is preferred (when possible) to recording a list of symptoms and signs. However, if a diagnosis is known and there are other symptoms or signs that are not generally part of the diagnosis, the diagnosis and each symptom or sign will be recorded separately.

#### **12.2.6. Adverse events based on examinations and tests**

The results from protocol mandated safety assessments will be summarized in the CSR.

Deterioration as compared to baseline in protocol mandated safety assessments should therefore only be reported as AEs if they fulfil any of the SAE criteria.

If deterioration in a vital sign or laboratory value is associated with clinical symptoms and signs, the symptom or sign will be reported as an AE and the associated vital sign or laboratory result will be considered as additional information.

Wherever possible the reporting investigator should use the clinical, rather than the laboratory term (e.g., anemia versus low hemoglobin value).

In the absence of clinical symptoms or signs, clinically relevant deteriorations in non-mandated parameters should be reported as AE(s).

Any new or aggravated clinically relevant abnormal medical finding at a physical examination as compared with the baseline assessment will be reported as an AE.

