### **7.6.3. Discontinuation of investigational medicinal product, individual stopping criteria and withdrawal from the study**

Subjects may discontinue treatment or may be withdrawn from the study for the following reasons:

- Healthy subject decision: The healthy subject is at any time free to discontinue treatment, without prejudice to further treatment.
- Withdrawal of consent: Subjects have the right to withdraw from the study at any time for any reason. If the withdrawal occurs following dosing with the study product, the subject will be asked to come for the follow-up examination.
- The subject will be withdrawn by the investigator,
  - If intercurrent illnesses occur, which, in the clinical judgment of the investigator or after discussion with the sponsor, may invalidate the study by interfering with the study product,
  - If it is discovered that the subject has entered the study in violation of the protocol,
  - If a significant protocol violation occurs during the study.

- Adverse event (AE), any significant and clinically relevant changes in the safety parameters which make continuation of IMP administration unjustified, at the discretion of the investigator. This includes but it is not limited to:
  - Any case of potential Hy's law (PHL) according to [Appendix 15.3](#)
  - Any case of a suspected severe gastrointestinal drug reaction
  - Any other severe or serious AE (SAE) that is judged as possibly related to the IMPs by the investigator
- Severe non-compliance to study protocol.

The reason(s) for withdrawal should be recorded on the appropriate page of the case report form (CRF) and the end of study form to be completed for each prematurely discontinued subject.

Subjects who discontinue the study will take part in a final follow-up examination including a physical examination, vital signs, ECG and standard safety laboratory tests, if possible. All subjects who drop from the study because of an AE or clinical laboratory abnormality will be followed-up at suitable intervals in order to evaluate the course of the AE or laboratory abnormality and to ensure reversibility or stabilization. The subsequent outcomes of these events will be recorded on the CRF.

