### **9.3. Safety measurements**

Safety and tolerability variables will be assessed by collection of data on AEs, vital signs, 12-lead ECG, laboratory assessments (hematology, clinical chemistry and urinalysis), pregnancy testing (females only), physical examination findings, body weight, performance of the Columbia-Suicide Severity Rating Scale (C-SSRS) and use of concomitant medication.

Viral serology, FSH (females only), and urine drugs of abuse, alcohol and cotinine will be assessed for eligibility.

For timing of assessments refer to the Schedule of Assessments in [Table 1](#).

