- If the start day and month are missing the date will be imputed as the first day of dosing in the known year unless the end date is known and shows that the AE ended before a dose was given in that year; in which case the start day and month will be imputed as 01Jan or with the date of Screening if this is later. If the end date is non-informative (i.e., is missing or does not contain enough information), the start date will be imputed as the first date of dosing in the known year. If the year is not a year of dosing then the date will be imputed as 01Jan or with the date of Screening if this is later.
- Missing times will be imputed as 00:00 h or with the time of dosing for events starting on a dosing day.

Adverse events will be summarized by treatment (where treatments will be pooled across the treatment periods) and overall, including tabulations by causality and severity (mild, moderate and severe). All tabulations will be presented by SOC and PT. Furthermore, listings of SAEs and AEs that led to withdrawal will be made and the number of subjects who

had any AEs, SAEs and AEs that led to discontinuation will be summarized. The AEs that occur before (first) dosing will be excluded from the summary tables.

The following information will be included in the listings: verbatim term, MedDRA SOC, PT and lowest level term, start date/time, end date/time, time from last dose, causality, action taken, whether the AE was classified as serious and the outcome.

All tabulations will include the number and percentage of subjects.

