#### **11.10.3. Resting 12-lead electrocardiogram**

12-Lead ECG results will be listed for each subject.

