## **12. ADVERSE EVENTS**

### **12.1. Definitions**

#### **12.1.1. Definition of adverse events**

An AE is the development of an undesirable medical condition or the deterioration of a pre-existing medical condition following or during exposure to a pharmaceutical product, whether or not considered causally related to the product.

An undesirable medical condition can be symptoms (e.g., nausea, chest pain), signs (e.g., tachycardia, enlarged liver) or the abnormal results of an investigation (e.g., laboratory findings, ECG).

In clinical studies an AE can include an undesirable medical condition occurring at any time after the subject/patient has signed informed consent, including run-in or washout periods, even if no specific treatment has been administered.

The term AE is used generally to include any AE whether serious or non-serious.

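### The AE reporting rule in Section 12.2.6 makes no exception for a symptom-free, non-serious test result that leads to withdrawal, so the count of AEs leading to discontinuation can miss a safety withdrawal

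*Protocol*

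**What the plan says.** Section 12.2.6 first states that "The results from protocol mandated safety assessments will be summarized in the CSR". From this it concludes that deterioration from baseline "in protocol mandated safety assessments should therefore only be reported as AEs if they fulfil any of the SAE criteria". Three sentences in the same section qualify the rule:

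- If a vital-sign or laboratory change comes with symptoms or signs, the symptom or sign is the AE.
- A clinically relevant deterioration in a parameter that the protocol does not mandate is an AE.
- A new or worsened clinically relevant physical examination finding is an AE.

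None of these deals with a change that leads to withdrawal.

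Section 9.3 lists vital signs, 12-lead ECG, hematology, clinical chemistry, urinalysis and the C-SSRS among the safety assessments. Section 12.1.1 counts as an undesirable medical condition "the abnormal results of an investigation (e.g., laboratory findings, ECG", with no seriousness threshold.

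Section 7.6.3 allows withdrawal for "any significant and clinically relevant changes in the safety parameters which make continuation of IMP administration unjustified", at the investigator's discretion. In the AE analysis (11.10.1), the number of subjects who "had any AEs, SAEs and AEs that led to discontinuation will be summarized". For ECG the whole analysis section (11.10.3) reads "12-Lead ECG results will be listed for each subject".

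**The concern.** The two sections set different thresholds. Withdrawal under 7.6.3 needs a clinically relevant change; an AE under 12.2.6 needs a serious one. A finding between the two can end a subject's participation without ever becoming an AE.

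Safety and tolerability is the only secondary objective (6.2), and the AE summaries, including AEs leading to discontinuation, are a main part of its analysis. An AE record also carries the investigator's causality and intensity ratings and is assigned to a treatment by its onset time. A withdrawal recorded without an AE has none of these. Nor can the gap be closed at the analysis stage: Section 11.1 says that no separate SAP will be written, and a finding that the site did not record as an AE is not in the AE data.

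**Working it through.** The protocol states no figure on this point, so the check sets its sections against each other.

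**1. Definition against reporting rule.** Section 12.1.1 admits abnormal laboratory and ECG results as AEs whether or not they are serious. Section 12.2.6 admits them, when symptom-free and from a mandated assessment, only if serious. The two sections give different answers for the same finding.

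**2. The path of one case.** Take a subject withdrawn for a symptom-free, non-serious ECG change.

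- 7.6.3: the withdrawal is permitted, since seriousness is not required.
- 12.2.6: the change is not reported as an AE.
- 12.2.3: causality, intensity and the yes/no item on withdrawal are variables collected for each AE. Without an AE there is nothing to attach them to.
- 11.10.1: the subject is not counted among those with an AE leading to discontinuation and, absent other events, not among those with any AE.
- 11.6: the subject is counted as withdrawn, with a reason.

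The disposition table would show a safety withdrawal that the AE table lacks.

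**3. Does the stated reason hold?** The rule rests on mandated results being summarized in the CSR.

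| Assessment | Planned presentation | Reason holds? |
|---|---|---|
| Vital signs (11.10.2) | Descriptive statistics by treatment and time-point, with change from baseline | Yes |
| Hematology, chemistry (11.10.4) | Summaries by treatment sequence and time-point, changes from baseline, shift tables | Yes, though not by treatment |
| ECG (11.10.3) | Listing only | No |
| Urinalysis (11.10.4) | Additional listing only | No |
| C-SSRS (11.10.6) | Listing only | No |

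General sentences elsewhere are broader: Section 11.2 speaks of summary statistics for all parameters, and the synopsis of summarizing all clinical safety laboratory data. The specific sections plan no summary for the last three rows, and the synopsis itself places ECG and C-SSRS among the data to be listed.

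ECG matters most here. Under the schedule of assessments, one ECG is taken 1.25 hours after each dose. Section 9.3.3 already requires the investigator to decide whether an abnormal ECG is clinically significant, but no planned table uses that judgment.

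**4. Scale per case.** With n subjects in the denominator, one missed subject with no other counted event lowers the overall subject percentage by 1/n.

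- All 44 randomized subjects dosed: 1/44 = 2.3 percentage points.
- 36 subjects: 1/36 = 2.8 percentage points.

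The number of such cases is not given and cannot be derived.

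**The case against.** The best defence is that the rule is a workable convention with several safeguards. Symptomatic changes enter as the symptom. Physical examination findings are AEs. Vital signs, hematology and chemistry have real summaries. Under 12.1.3 a medically qualified sponsor expert reviews AEs, vital signs, laboratory and other safety data for other significant AEs to be reported in the CSR. Appendix 15.3 requires sponsor notification when ALT or AST reaches 3 times the upper limit of normal, and turns agreed or unresolved Hy's Law cases into SAEs. After the first dose, scheduled safety laboratory tests occur only before dosing in period 3 and at follow-up. Sections 7.6.3 and 7.6.4 name AEs and safety-parameter changes as separate reasons, so the two tables could differ by design. The safety analysis is descriptive, in healthy subjects given single doses.

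Most of this stands, and it narrows the point. It does not close the gap. The expert review depends on later judgment and creates no investigator-assessed AE. The Hy's Law process needs both an aminotransferase and a bilirubin criterion, so an isolated enzyme rise does not become an SAE by that route. Naming two withdrawal reasons does not explain why a safety withdrawal should carry no causality rating.

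A reader might infer more than the protocol supports:

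- *That discontinuations as a whole are undercounted.* Section 11.6 counts every withdrawal with its reason.
- *That physical examination findings are lost.* Section 12.2.6 makes clinically relevant ones AEs.
- *That an unscheduled test is held to a stricter standard than a scheduled one.* The text concerns parameters that are not mandated; an extra ECG or repeat laboratory test still measures a mandated one.
- *That the ECG judgment is only normal or abnormal.* Section 9.3.3 also requires clinical significance and the reason to be addressed.
- *That the 8 losses allowed between 44 and 36 subjects measure the undercount.* That allowance covers every cause.

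**Conclusion.** The point holds in a limited form. Section 12.2.6 conflicts with the AE definition in 12.1.1 and does not fit 7.6.3. A withdrawal for a symptom-free, non-serious laboratory, ECG or vital-sign change would be missing from the count of AEs leading to discontinuation while appearing in the disposition table. The reason given for the rule fails for ECG, urinalysis and the C-SSRS.

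This is conditional: the count is short only if such a case occurs, and the protocol gives no basis for saying how often. The 2.3 to 2.8 points per case assume 44 to 36 subjects in the denominator and no other counted event in the affected subject.

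The protocol does not support requiring every change judged clinically significant to be an AE. That is a choice between reporting conventions. The case for change rests on the findings that end a subject's participation.

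**What to change.** Reconcile 12.2.6 with 12.1.1, 7.6.3 and 11.10.1 by adding one sentence to 12.2.6: deterioration in a protocol-mandated assessment is also reported as an AE when it is the reason for discontinuing IMP or for withdrawing from the study. This concerns reporting only and leaves the withdrawal criteria as they are.

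In 11.10.3, add a by-treatment count of subjects with a post-dose ECG judged abnormal and clinically significant. Section 9.3.3 already requires the judgment, but names only the overall normal/abnormal evaluation as reported in ClinBase. It should therefore state that clinical significance is captured there too.

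The cost is slightly more AE records, one data item to confirm and one small table. No extra assessment or subject is needed.

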### **12.3. Reporting of serious adverse events**

All SAEs have to be reported, whether or not considered causally related to the IMP, or to the study procedure(s). All SAEs will be recorded in ClinBase.

If any SAE occurs in the course of the study, then investigators or other clinical unit personnel will inform appropriate AstraZeneca representatives immediately, or **no later than 24 hours** of when he or she becomes aware of it.

The designated AstraZeneca representative will work with the investigator to ensure that all the necessary information is provided to the AstraZeneca Patient Safety Data Entry Site **within 1 calendar day** of initial receipt for fatal and life-threatening events and **within 5 calendar days** of initial receipt for all other SAEs.

For fatal or life-threatening AEs where important or relevant information is missing, active follow-up will be undertaken immediately.

Investigators or other clinical unit personnel will inform AstraZeneca representatives of any follow-up information on a previously reported SAE immediately, or **no later than 24 hours** of when he or she becomes aware of it.

In addition to recording of SAEs in ClinBase, the AstraZeneca Serious Adverse Event Report – Clinical Study form for reporting an SAE to the Data Entry Site (DES) will also be used.

All information provided for the SAE sent into the DES will be in English.

The following CRF modules will be completed for each SAE report:

- Demography
- Dosing
- AE (including start and stop date/time for the AE, the investigator's causality assessment to study drug, action taken with study drug, severity and outcome)

- 
- SAE (including serious criteria, causality assessment to study procedure any investigations, the symptoms and course of the event and any treatments given)
  - Medical History
  - Concomitant Medications
  - LIVERRF (risk factors), LIVERSS (signs and symptoms) and LIVERDI (additional diagnostic with results) for all SAEs with a reported term of ‘potential Hy’s Law’ or ‘Hy’s Law’ will be provided in a narrative form by the PI
  - Any additional supporting information e.g., laboratory test results, vital signs, ECG assessments

The ‘AstraZeneca first aware date’ for all SAEs reported is the date that any member of the Provider or AstraZeneca first become aware of the SAE and for regulatory reporting purposes this is the ‘clock start date’.

Each SAE (as Portable Document Format [PDF]) should be sent to the DES Tata Consultancy Services (TCS) preferably via secure e-mail using the mailbox e-mail address: [contact]

The e-mail should contain the following information in the e-mail header:

Subject Title: New SAE; <study code>, <SAE text>, <Country>, <Centre No>, <Enrolment code>, <Randomization code>

The message in the e-mail itself should contain the following:

A NEW serious adverse event has been reported for the following subject:

Study Code:

Country: <country>

Centre No: <study site number>

Enrolment Code: <SUBJECT>

Randomization Code: <SUBJECT>

SAE Description:

Seriousness Criteria:

Study Drug Causality/Additional Med Causality/other Med Causality/Study Procedure Causality

Date SAE met criteria for serious:

AZ (= PAREXEL investigator) first aware date:

### **13. LEGAL AND ADMINISTRATIVE ASPECTS**

#### **13.1. Archiving of study documentation**

All source documents generated in connection with the study will be retained in the limited access file storage area, respecting the privacy and confidentiality of all records that could identify the subjects. Direct access is allowed only for authorized people for monitoring and auditing purposes. Source documents will be handled, stored and archived according to in-house procedures.

Investigator specific essential documents will be retained until at least 2 years after the last approval of a marketing application in an ICH region and until there are no pending or contemplated marketing applications in an ICH region or at least 2 years have elapsed since the formal discontinuation of clinical development of the IMP. These documents could be retained for a longer period however, if required by the regulatory requirements or by an agreement with AstraZeneca. It is the responsibility of AstraZeneca to inform the investigator as to when these documents no longer need to be retained.

Study documentation will be archived by the CRO for 15 years.

#### **13.2. Publication of study results**

If a publication (e.g., in a scientific journal) based on the results of this study is envisaged, approval from AstraZeneca will be obtained and a draft manuscript will be submitted to AstraZeneca for scrutiny and comment. The choice of conduit will be mutually agreed on by the PI and AstraZeneca.

#### **13.3. Clinical study report**

An integrated CSR will be prepared in accordance with the standards of the ICH guideline for structure and content of clinical study reports (ICH E3). Copies of the CSR will be provided to the IEC/IRB and the national regulatory authority in accordance with regulatory requirements and PAREXEL SOPs. In the event of premature termination of the study or other conditions specified in ICH E3, an abbreviated CSR may be prepared.

## **15. APPENDICES**

### **15.1. Additional Safety Information**

#### **FURTHER GUIDANCE ON THE DEFINITION OF A SERIOUS ADVERSE EVENT**

##### **Life-threatening**

‘Life-threatening’ means that the subject was at immediate risk of death from the adverse event (AE) as it occurred or it is suspected that use or continued use of the product would result in the subject’s death. ‘Life-threatening’ does not mean that had an AE occurred in a more severe form it might have caused death (e.g., hepatitis that resolved without hepatic failure).

##### **Hospitalization**

Outpatient treatment in an emergency room is not in itself a serious adverse event (SAE), although the reasons for it may be (e.g., bronchospasm, laryngeal edema). Hospital admissions and/or surgical operations planned before or during a study are not considered AEs if the illness or disease existed before the subject was enrolled in the study, provided that it did not deteriorate in an unexpected way during the study.

##### **Important medical event or medical intervention**

Medical and scientific judgment should be exercised in deciding whether a case is serious in situations where important medical events may not be immediately life-threatening or result in death, hospitalization, disability or incapacity but may jeopardize the subject or may require medical intervention to prevent one or more outcomes listed in the definition of serious. These should usually be considered as serious.

Simply stopping the suspect drug does not mean that it is an important medical event; medical judgment must be used.

Examples of such events are:

- Angioedema not severe enough to require intubation but requiring intravenous hydrocortisone treatment.
- Hepatotoxicity caused by paracetamol/acetaminophen overdose requiring treatment with N-acetylcysteine.
- Intensive treatment in an emergency room or at home for allergic bronchospasm.
- Blood dyscrasias (e.g., neutropenia or anemia requiring blood transfusion) or convulsions that do not result in hospitalization.

- Development of drug dependency or drug abuse.

## **A GUIDE TO INTERPRETING THE CAUSALITY QUESTION**

The following factors should be considered when deciding if there is a “reasonable possibility” that an AE may have been caused by the investigational medicinal product (IMP).

- **Time Course / Exposure to suspect drug**

Has the subject actually received the suspect drug? Did the AE occur in a reasonable temporal relationship to the administration of the suspect drug?

- **Consistency with known drug profile**

Was the AE consistent with the previous knowledge of the suspect drug (pharmacology and toxicology) or drugs of the same pharmacological class? OR, could the AE be anticipated from its pharmacological properties?

- **Dechallenge experience**

Did the AE resolve or improve on stopping or reducing the dose of the suspect drug?

- **No alternative cause**

The AE cannot be reasonably explained by other aetiology such as the underlying disease, other drugs, other host or environmental factors.

- **Rechallenge experience**

Did the AE reoccur if the suspected drug was reintroduced after having been stopped?

*Note: AstraZeneca would not normally recommend or support a rechallenge.*

- **Laboratory tests**

A specific laboratory investigation (if performed) has confirmed the relationship?

A “reasonable possibility” could be considered to exist for an AE where one or more of these factors exist.

In contrast, there would not be a “reasonable possibility” of causality if none of the above criteria apply or where there is evidence of exposure and a reasonable time course but any dechallenge (if performed) is negative or ambiguous or there is another more likely cause of the AE.

In difficult cases, other factors could be considered such as:

- Is this a recognized feature of overdose of the drug?
- Is there a known mechanism?

Ambiguous cases should be considered as being a “reasonable possibility” of a causal relationship, unless further evidence becomes available to refute this. Causal relationship in cases where the disease under study has deteriorated due to lack of effect should be classified as no reasonable possibility.

---

